Pharmacologic and Clinical Properties of Doxazosin. Doxazosin is a quinazoline compound that is a selective inhibitor of the alpha-1 subtype of alpha-adrenergic receptors. The chemical name is 1-(4-amino-6,7-dimethoxy-2-quinazolinyl)-4-(1,4-benzodioxan-2-ylcarbonyl) piperazine methanesulfonate. The molecular formula for doxazosin is $C_{23}H_{25}N_5O_5 \cdot CH_4O_3S$ and the molecular weight is 547.6. Doxazosin is used clinically to treat hypertension and improve urination in men with benign prostatic hyperplasia. Peak plasma levels occur at 2-3 hours after oral administration. Plasma elimination of doxazosin is biphasic, with an elimination half-life of 22-30 hours, which is not influenced by age, renal function or dose. Doxazosin is available in the U.S. as a prescription product for oral use. The most frequently reported adverse reactions include headache (10-14%), dry mouth (2-11%), tiredness (5-12%), dizziness (15%), hypotension (1.7%) and nausea/vomiting (2-4%) (De Jong et al., 2010; Shorter et al., 2013).

RESEARCH DESIGN AND METHODS

Overview. This study is a Stage II double-blind, 12-week, randomized controlled trial of the effects of the alpha-1 adrenergic antagonist, doxazosin (immediate release formulation), as compared to placebo in reducing PTSD symptomatology and substance use severity in Veterans with co-occurring PTSD and substance use disorders (SUD). Participants may also complete neuroimaging scanning sessions prior to and following treatment.

Subjects. Participants will be 144 treatment-seeking Veterans with current PTSD and SUD. Subjects taking psychotropic medications will be required to be maintained on a stable dose for at least four weeks or more, based on clinical judgment, before treatment initiation. Primary exclusions include bipolar disorders; previous treatment with doxazosin; adverse reactions to quinazolines or other alpha-1-antagonists; and abnormal liver function tests. Additional inclusion and exclusion criteria can be found in the Human Subjects section.

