Power. This study is powered to estimate the effects of doxazosin on significant reduction in PTSD symptoms at the end of treatment (see Hypothesis 1), and increased abstinence rates at the end of treatment (see Hypothesis 2). Placebo rates of reduction in CAPS scores are conservatively estimated to be 20% (Zohar et al., 2002). In a small pilot study, De Jong et al. (2010) found ~31% reduction in CAPS scores using 4mg doxazosin. A sample of 100 participants will provide 80% power with a .05 type 1 error rate to detect a difference in the reduction of CAPS scores between doxazosin (31±20%) and placebo (20±20%). Placebo rates of drug abstinence are estimated from established double-blind placebo controlled trials. Continuous abstinence from weeks 9-12 is observed in 10-15% of treatment seekers without co-occurring PTSD (Shorter et al., 2013) so we anticipate an attenuated rate of 5-10% in the placebo group. Although there is limited information on the effectiveness of doxazosin in addiction, a sample of 100 subjects (50 in each arm) will provide adequate power to detect an abstinence rate as low as 32% in the doxazosin when the placebo cessation rate is 10% and as low as 23% when the placebo rate is 5%. Due to the nature of the study population, we anticipate ~30% dropout rate; thus the number of subjects randomized is inflated to 144, n=72 randomized to each treatment arm of the study.

Power calculations for the neuroimaging component are based on previous studies of individuals with PTSD or substance use disorders. Based on our previous work and the extant literature, we conservatively estimate that approximately 88/144 will be eligible and volunteer to participate in the neuroimaging component. Of these 88 participants, half (n=44) will be assigned to doxazosin and half to placebo (n=44). Hypotheses 3A and 3B will, therefore, involve the subset of 44 participants who complete the neuroimaging component and receive doxazosin treatment. A recent study of Veterans with PTSD (n=14) as compared to controls (n=15) observed significant differences in PFC-AMY resting state connectivity (Sripada et al., 2012). The effect size for this difference was 0.8 (measured using Cohen's d). Thus, power (1- β) reaches .80 with a total sample size of N=26 (two-tailed, alpha=.05). Another recent study of cocaine-dependent individuals (N=45) found that

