Hypothesis 2: Participants who receive doxazosin, as compared to placebo, will evidence significantly greater reductions in SUD severity. To test this hypothesis, logistic regression analysis will be used to examine rates of abstinence (TLFB, biological tests) during the end of treatment phase (week 9-12). Weekly point prevalence abstinence will be examined using generalized linear models under a generalized estimating equations (GEE) framework. GEE models will allow for examination of differential effects of doxazosin vs. placebo on abstinence over the course of the treatment phase of the study. Weekly abstinence (yes/no) as well as amounts (e.g., standard drink units, dollar amount of substances) will be examined over time to determine if treatment is effective in reducing substance use when abstinence is not achieved.

Hypothesis 3A: PFC-AMY connectivity at rest and in response to trauma vs. neutral cues will predict amount of change in PTSD symptoms (CAPS-5).

Hypothesis 3B: PFC-AMY connectivity at rest and in response to substance vs. neutral cues will predict time to first use of alcohol or drugs (TLFB).

The following preprocessing and analytical parameters will be used to test hypotheses 3A-3B. **Preprocessing:** Post-acquisition preprocessing and statistical analysis of all of imaging data will be performed using FEAT (fMRI Expert Analysis Tool) Version 5.98, part of FSL (FMRIB's Software Library). Data will be preprocessed using scripting tools from FEAT. Non-brain signal will be removed using FSL's BET brain extraction. Scans will be corrected for motion using FSL's linear registration and scans will be spatially smoothed using a Gaussian kernel of 8 mm FWHM. Participants with head motion ≥ 0.2 mm will be excluded from the analyses [1]. Motion artifacts will be identified and scrubbed from each subject's data. Scans will be spatially co-registered with a standardized anatomical template (Montreal Neurological Institute) using a 12 parameter affine transformation.

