1. RISKS TO SUBJECTS

Drs. [name], [name], [name], [name], [name] and [name] have all completed the University of Miami computer-based CITI Human Subjects Research Education Course. The research team includes two licensed clinical psychologists (Drs. [name], PI and [name], Co-I) and two board certified psychiatrists (Co-Is, Drs. [name] and [name]) with extensive clinical research experience in posttraumatic stress disorder (PTSD) and substance use disorders. [name] (Co-I) also has clinical research experience in posttraumatic stress disorder (PTSD), alcohol use disorders (AUD), and neuroimaging. [name] has expertise in neuroimaging. All research activity, informed consents and continuing reviews will be reviewed by the Medical University of South Carolina (MUSC) Institutional Review Board (IRB) and the Ralph H. Johnson VAMC Office of Research

and Development (R&D) committee, in compliance with 45CFR46 before the research is initiated. Continuing review will occur annually.

Human Subjects Involvement and Characteristics

A total of 144 adults will be recruited over a 4-year period. The inclusion/exclusion criteria are as follows:

Inclusion Criteria:

1. Male or female; any race or ethnicity.
2. Served in U.S. Military – any branch or operation.
3. Subjects must be able to comprehend English.
4. Meet criteria for current (i.e., last 6 months) Substance Use Disorder (SUD) using a modified version of the MINI 7.0 (i.e., must meet DSM-5 criteria for SUD in the past 6 months instead of 12 months).
5. Meet DSM-5 criteria for current (i.e., last month) PTSD.
6. Subjects taking psychotropic medications will be required to be maintained on a stable dose for at least four weeks before treatment initiation. This is because initiation or change of medications during the course of the trial may interfere with interpretation of results.
7. Must consent to random assignment to doxazosin or placebo.
8. Must consent to complete all treatment and follow-up visits.

Exclusion Criteria:

1. Subjects meeting DSM-5 criteria for current bipolar affective disorders, as the study protocol may be therapeutically insufficient.
2. Subjects experiencing significant withdrawal symptoms, as evidence by a score of 10 or above on the Clinical Institute Withdrawal Assessment of Alcohol (CIWA). These subject will be referred for clinical detoxification and may be re-assessed for study eligibility after medically supervised detoxification has been completed.

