2. ADEQUACY OF PROTECTION FROM RISK

Recruitment and Informed Consent

Participants will be primarily recruited from the Ralph H. Johnson VAMC and affiliated CBOCs' Substance Treatment and Recovery (STAR) program. [name] (PI) is a Staff Psychologist in the STAR. Potential study participants will be told about the study at STAR intake, the program orientation session, and at weekly group therapy meetings, and provided with a telephone number to call and receive more information. IRB-approved flyers and brochures describing the study and providing contact information will be placed in each of the STAR group therapy rooms, in each of the STAR clinician and case manager offices, and in the STAR program waiting room. We will also post IRB-approved recruitment flyers in prominent locations in other VA hospital clinics (e.g.,

internal medicine, women's health, PTSD clinic, pain clinic, emergency department) and other satellite clinics within the Charleston VAMC catchment area. The research team has used these methods successfully in the past to recruit Veterans to various clinical protocols.

While recruitment will be primarily from the STAR, we will also place IRB-approved recruitment flyers in prominent locations in affiliated community based outpatient clinics (CBOC) and throughout the MUSC hospital, including the Center for Drug and Alcohol Programs, and the National Crime Victims Treatment Center.

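### Eligibility requires no recent use, so Veterans already abstinent at entry can be enrolled and, if they stay abstinent, count as weeks 9-12 successes under Hypothesis 2 without any reduction in use

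*Combined protocol and SAP*

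**What the plan says.** The Subjects paragraph of Research Design and Methods states: "Participants will be 144 treatment-seeking Veterans with current PTSD and SUD". In the Human Subjects section, inclusion criterion 4 defines current SUD: "Meet criteria for current (i.e., last 6 months) Substance Use Disorder (SUD) using a modified version of the MINI 7.0". PTSD, by contrast, must be current in the last month (criterion 5). None of the inclusion or exclusion criteria sets a minimum of recent use or excludes people who are already abstinent. The baseline TLFB, covering 60 days, and the baseline ethyl glucuronide, urine drug screen and breathalyzer tests are collected, but none of them is an entry criterion for recent use.

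Hypothesis 2 is that participants on doxazosin "will evidence significantly greater reductions in SUD severity". Its first-named test is: "logistic regression analysis will be used to examine rates of abstinence (TLFB, biological tests) during the end of treatment phase (week 9-12"). Weekly abstinence is also analysed by GEE, and amounts used "will be examined over time to determine if treatment is effective in reducing substance use when abstinence is not achieved". No baseline-use term is named in any of these models. Under General, all analyses use all randomized subjects. Under Randomization, the urn factors are PCL and AUDIT total scores.

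The Power paragraph starts from 10-15% continuous abstinence among treatment seekers in an earlier trial, "so we anticipate an attenuated rate of 5-10% in the placebo group". It then treats 50 per arm as adequate for 32% versus a placebo cessation rate of 10%, or 23% versus 5%.

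**The concern.** The entry window (6 months) is longer than the window in which baseline use is measured (60 days). Someone whose last use was about 120 days before baseline falls inside the first and outside the second. That person has zero baseline use, cannot show a reduction, and is scored a success in weeks 9-12 simply by remaining as they were. The hypothesis speaks of reduction and the power paragraph of cessation, and both presuppose use at entry.

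If such entrants are more than a few, the abstinence endpoint becomes a mixture of achieving abstinence and maintaining abstinence reached before randomization. A positive result could not be attributed clearly to either, and a null result could reflect a higher base rate as much as an inactive drug. The AUDIT total does not protect against this, because it is a severity score and not a record of recent use. The amounts and GEE analyses help only in part, since a person with zero baseline use cannot reduce there either.

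**Working it through.** **Inputs.** From the Power paragraph: 50 evaluable per arm; 10% versus 32% and 5% versus 23%; about 30% dropout; 144 randomized. The .05 error rate is stated for the CAPS comparison. For abstinence the text says only that power is adequate. I assume a two-sided .05 test and an 80% target.

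**1. The plan's own figures.** Arcsine approximation: power = Φ(h·√(n/2) − 1.96), with h = 2(asin√p₂ − asin√p₁).
- 10% vs 32%: h = 0.559; 0.559 × 5 − 1.96 = 0.835; power 0.798.
- 5% vs 23%: h = 0.549; 0.549 × 5 − 1.96 = 0.787; power 0.784.
- Dropout: 100/0.70 = 143, against 144 stated.

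The plan's figures reproduce. Exact binomial enumeration of the pooled z-test gives 0.80 and 0.79, and I use that method below.

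**2. Adding entrants already abstinent.** Let f be the share abstinent at entry and s the share of these who are abstinent in weeks 9-12 on placebo. Neither is in the documents, so both are assumptions. Each arm's rate is (1 − f) × (rate in active users) + f × (rate in abstinent entrants). For f = 20% and s = 0.5, starting from 10% vs 32%:
- Placebo: 0.8 × 0.10 + 0.2 × 0.50 = 0.18.
- Doxazosin, no effect in abstinent entrants: 0.8 × 0.32 + 0.2 × 0.50 = 0.356.
- Doxazosin, same absolute effect: 0.256 + 0.2 × 0.72 = 0.40.
- Doxazosin, same odds ratio: OR = (0.32/0.68)/(0.10/0.90) = 4.24; rate in abstinent entrants 4.24/5.24 = 0.81; arm rate 0.256 + 0.2 × 0.81 = 0.418.

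Power at 50 per arm, s = 0.5 (0.80 at f = 0):

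| f | Placebo rate | Same odds ratio | Same absolute effect | No effect |
|---|---|---|---|---|
| 10% | 14% | 0.77 | 0.74 | 0.66 |
| 20% | 18% | 0.75 | 0.69 | 0.52 |
| 30% | 22% | 0.75 | 0.65 | 0.39 |

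**3. Sensitivity to s, at f = 20%.**
- s = 0.3 (placebo 0.08 + 0.06 = 14%): power 0.82 (same odds ratio), 0.74 (same absolute effect), 0.57 (no effect).
- s = 0.7 (placebo 0.08 + 0.14 = 22%): about 0.65, 0.65 and 0.48.

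So there need be no loss at all if the odds ratio is common and few abstinent entrants stay abstinent. The loss is large only if the drug does nothing for them.

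**4. The 5% vs 23% scenario**, f = 20%, s = 0.5 (0.79 at f = 0). Placebo is 0.04 + 0.10 = 14%. With OR = (0.23/0.77)/(0.05/0.95) = 5.68, the rate in abstinent entrants is 5.68/6.68 = 0.85. Power is 0.72 (same odds ratio), 0.58 (same absolute effect) and 0.43 (no effect).

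**5. Options for analysis.** Restricting the test to baseline users at f = 20% leaves 0.8 × 50 = 40 per arm, with power 0.70 for 10% vs 32%. Keeping everyone and adding baseline use status to the logistic model raised power in simulation by about 3 to 10 points over the unadjusted model (10% vs 32%, s = 0.5, f from 10% to 30%).

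**The case against.** The strongest case on the other side is that the documents permit such entry but do not show that it happens. The population is described as treatment-seeking with current SUD, and the diagnostic window has already been narrowed from 12 months to 6. This stands: no size can be attached without assuming f.

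A reader might infer more, on four counts that the documents do not support.
- **The placebo rate.** One might say that 5-10% leaves no room for abstinent entrants. It is derived from an earlier trial of treatment seekers, and whether that sample included people abstinent at entry cannot be seen from here. If it did, adding f on top would count them twice.
- **Detoxification.** Those with significant withdrawal "may be re-assessed for study eligibility after medically supervised detoxification has been completed". They were drinking recently, and unless re-assessment is long delayed they will have use days in the 60-day TLFB. This route adds little.
- **Recruitment.** The plan says "Potential study participants will be told about the study at STAR intake, the program orientation session, and at weekly group therapy meetings", which could bring in people already in recovery. But intake and orientation are in the same list, and the Recruitment paragraph adds a primary care mental health clinic, letters, flyers, advertisements and referrals.
- **The worst-case power.** The fall to 0.39 assumes no drug effect in abstinent entrants. The plan treats relapse as part of its target: Hypothesis 3B uses time to first use. An effect on maintenance is therefore plausible, and the losses are then smaller.

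It can also be said that the weekly GEE and amounts analyses, and the fallback indices under Problems and Alternative Strategies, look beyond abstinence. They soften the problem but name no baseline-use term.

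**Conclusion.** The gap is real: eligibility does not require recent use, and the Hypothesis 2 endpoint does not distinguish stopping from staying stopped. The arm contrast remains unbiased by randomization, so this concerns interpretation and precision, not validity. If 20% entered abstinent and half of those on placebo stayed so, power for 10% versus 32% would be 0.75, 0.69 or 0.52, depending on the drug's effect in them, against 0.80. These figures rest on assumed f and s, a two-sided .05 test and 50 evaluable per arm. The documents do not support saying that abstinent Veterans make up any particular share of the sample, or that the test is biased. The change is advisable and cheap, but not a condition for a valid trial.

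**What to change.** 1. Define baseline use status from the TLFB already administered, for example any use in the 30 days before baseline (yes/no).
2. Add it as an urn factor if enrolment allows.
3. Prespecify it as a covariate in the Hypothesis 2 logistic and GEE models, fitted to the full intent-to-treat sample. The adjusted odds ratio is conditional on baseline use, so report the plain abstinence rates by arm beside it.
4. Report the frequency of baseline use status by arm.
5. Prespecify a sensitivity analysis in participants using at baseline, and report maintenance of abstinence separately in the others.

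The cost is one more urn factor (four combinations become eight), one model term and a few sentences in the analysis section, fixed before unblinding. No new assessment is needed. The sensitivity analysis has a smaller sample (40 per arm at f = 20%).

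A recent-use entry criterion would also work, but it narrows the recruitment pool and changes the population, so it is an option for the sponsor. Making baseline users the primary Hypothesis 2 set is not recommended: it departs from the stated intent-to-treat rule and, at f = 20%, its power of 0.70 is below the 0.75 of the full sample under a common odds ratio.

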2. ADEQUACY OF PROTECTION FROM RISK

Recruitment and Informed Consent

Participants will be primarily recruited from the Ralph H. Johnson VAMC and affiliated CBOCs' Substance Treatment and Recovery (STAR) program. [name] (PI) is a Staff Psychologist in the STAR. Potential study participants will be told about the study at STAR intake, the program orientation session, and at weekly group therapy meetings, and provided with a telephone number to call and receive more information. IRB-approved flyers and brochures describing the study and providing contact information will be placed in each of the STAR group therapy rooms, in each of the STAR clinician and case manager offices, and in the STAR program waiting room. We will also post IRB-approved recruitment flyers in prominent locations in other VA hospital clinics (e.g.,

internal medicine, women's health, PTSD clinic, pain clinic, emergency department) and other satellite clinics within the Charleston VAMC catchment area. The research team has used these methods successfully in the past to recruit Veterans to various clinical protocols.

While recruitment will be primarily from the STAR, we will also place IRB-approved recruitment flyers in prominent locations in affiliated community based outpatient clinics (CBOC) and throughout the MUSC hospital, including the Center for Drug and Alcohol Programs, and the National Crime Victims Treatment Center.

The research team and all of the study staff have completed (or will complete upon hiring) the Miami Collaborative IRB Training Initiative (CITI) course and its associated tests in research ethics. Informed consent (IC) will be collected at the study research offices, in a private and interruption-free environment. The PI, Co-Is, Study Coordinator, or other trained research staff will obtain IC. The IC form will outline: a) the sponsorship of the study; b) the nature, purpose and procedures of the study; c) the voluntary nature of participation (i.e., participation is not required; participation can be discontinued at any time); d) the duration of the study; e) potential risks and discomforts, as well as benefits of participation; f) that all information will be kept confidential subject to the provisions of the state and federal law; g) compensation; and h) alternative treatments. The IC form will specifically review the potential for psychological distress, and the risks associated with fMRI and doxazosin that may occur as a result of study participation. The IC form will be explained to participants in easy-to-understand language, and participants will be instructed to read the form carefully prior to signing it. The IC form will include emergency contact information for the PI ([name]). Any questions pertaining to the study or consent process will be answered fully. Potential participants will not be required to make a decision to participate at the initial contact, though that possibility will be available. If participants wish to discuss study participation with their family and/or significant others, they will be encouraged to do so. Participants will be informed that they can discontinue their participation in the study at any time and that this decision will not influence the care they receive at the VAMC or MUSC clinics. Consent will be documented by the signature of the participant on the IC document, accompanied by the signature of the individual obtaining the consent. Participants will be given a copy of the informed consent. Research staff will document the informed consent process in the medical record of the participant.

Protection Against Risk

We will take careful precautions to maintain confidentiality for all participants, using procedures that we have successfully employed in similar previous as well as ongoing studies with Veterans. The investigators and all study personnel will sign a confidentiality agreement that no identifying information of specific individuals will appear in any internal reports or external documents (e.g., peer-reviewed publications, presentations). All study data related to psychological outcomes (i.e., the participant responses to questionnaires) and demographics will not have any unique identifying data attached in any way. There will be no linkage between a participant's identity and their responses. There will be only one master list of participants (again, not linked to any participant responses) which will be kept locked separate from all data and will be available only to the PI, Co-Is and approved study personnel. All data will be stored in a confidential manner (i.e., in locked files or on encrypted computers in the Study Coordinator's or RA's research office) so as to protect the confidentiality of participant information. Access to research records (paper and computerized) will be restricted to the project staff. Specifically, access to de-identified study data will be limited to named project investigators, the Study Coordinator, sponsor audit personnel, VAMC R&D auditors, and MUSC IRB auditors. Neuroimaging data will be stored on a secure password protected server maintained by MUSC's Center for Biomedical Imaging (CBI). Only Drs. [name], [name], and [name] will have access to the files on the secure CBI server. The PI, Co-Is and study personnel have completed (or will complete upon hiring) a certified program of instruction in the protection of human subjects in research, such as the VA website tutorial or the University of Miami CITI course. These courses in the responsible conduct of research and the protection of human subjects will be completed on an annual basis, in compliance with VA and MUSC regulations.

In addition, a Research Monitor has been selected for the present study. The Research Monitor, [name], M.D. will oversee the safety of the research and report observations/findings to the IRB or a designated institutional official. The Research Monitor will review all unanticipated problems involving risks to subjects or others associated with the protocol and provide an independent report of the event to the IRB. The Research Monitor may discuss the research protocol with the investigators; shall have authority to stop a research protocol in progress, remove individual human subjects from a research protocol, and take whatever steps are necessary to protect the safety and well-being of human subjects until the IRB can assess the monitor's report; and shall have the responsibility to promptly report their observations and findings to the IRB or other designated official and the Human Research Protection Office (HRPO).

Risks associated with assessment include the possibility that participants might be upset by questions pertaining to trauma, alcohol or drug use, or their emotional functioning. The research team will closely monitor for any increase in distress at every treatment visit. Substance use, PTSD, anxiety and depression symptoms will be monitored weekly using standardized measures in order to detect any symptom worsening requiring further evaluation. Additionally, participants will be advised to observe any signs of worsening PTSD, substance use and depression symptoms and to discuss these with the research team. All participants will be informed at the outset that they may terminate participation at any point. If a participant becomes upset in-between visits, he or she will be encouraged to contact the Study Coordinator, his or her case manager at the VA, and/or [name]. If a participant needs or desires immediate attention, arrangements will be made for an appointment with an experienced mental health provider. The informed consent document provides direction to contact the study staff during office hours and/or the Emergency Room at any time for worsening of symptoms.

Our past research suggests that data collection using many of these measures can be conducted without undue psychological distress or exacerbation of symptoms among adult participants. This experience includes substantial research with younger and older adults, military service members, rape victims, victims of other forms of violence, and work on large-scale studies asking questions about similar topics with general population samples. In addition, it includes Veterans with alcohol, cocaine, marijuana and/or opioid use disorders. In the event that participants experience extreme psychological distress secondary to participation, they will be encouraged to telephone the PI. In addition, they will have access to urgent care services at the Charleston VAMC and CBOC locations. Any adverse events occurring among randomized participants will be reported to the PI, who will then report these adverse effects in writing to the VA R&D Committee, MUSC IRB, and the study sponsor per protocol (see the Data Safety and Monitoring Plan at the end of this section for more details). The research team is comprised of licensed clinical psychologists and psychiatrists with extensive experience working with adults who have experienced significant life stressors and addiction. If project staff believes that a participant is significantly distressed by participation, the PI will be notified and will contact the participant immediately to assess distress and assure participant safety. If called by a participant, the PI will attempt to address all participant concerns and will set up an alternate referral for counseling for those who desire it from outside the project. All participants will review, at the initiation of participation, an informed consent document which specifically reviews potential psychological distress as a potential outcome of participation. If necessary, they will be asked to complete a safety plan and agree to call the project staff or 911. However, if safety is in question in the minds of any project staff, the Mobile Crisis unit of Charleston County, which involves a team of police and psychiatric workers, or the EMS unit will be dispatched to the participant's home to assure safety. In our NIH and DoD-funded clinical trials of comorbid PTSD and substance use disorder treatment provision, we have not had any problems related to participation that could not be safely resolved with these methods.

A portion of the history and physical examination for participants at affiliated CBOC locations may be performed via telemedicine, if necessary. Research staff at the CBOC will take vital signs, including orthostatic blood pressure and pulse measurements, each week. In addition, all participants will receive an electrocardiogram at baseline and a complete metabolic panel to include liver and renal function tests to ensure study eligibility. A medical clinician on the research project may meet with the participant via telemedicine to assess medical and related history (e.g., social, surgical, family history) and review of systems. Whenever the history and physical

examination is conducted in part utilizing telemedicine we will include two additional steps to ensure patient safety and determine eligibility to enroll in the study: 1) a study physician will review the CPRS records to identify any potential medical or other exclusions, and 2) the research staff will view alert and/or call the participant's primary care doctor and ask if they have any concerns with the individual participating in the doxazosin study. The study medication (doxazosin) is an approved agent with a long safety record; thus, we do not anticipate any problems utilizing telemedicine to complete part of the history and physical examination. Furthermore, it is expected that only a small proportion of history and physical examinations will occur via telemedicine. However, because telemedicine is different than the standard of care, we have decided to add in these additional measures to ensure patient safety.

All relevant study staff will be required to complete the CBI's MRI safety training class. The course is taught by an American Registry of Radiologic Technologists registered technician. The staff will be trained about safety in the MRI environment, and how to screen oneself and others. The staff will also have knowledge of safety procedures for entering the scanner facility, safely removing participants from the scanner, when and how to quench the magnet and basic emergency procedures including emergency contact information. Standard operating procedures for emergency situations are located on-site. The MRI technician and Drs. [name] and [name] (Co-Is) are authorized to operate the equipment and will be present or available during the scanning sessions. Although there are no known risks of MRI scanning to a developing fetus at 3.0 T, the possibility that risks could be discovered in the future cannot be ignored. Therefore, urine pregnancy tests will be used to exclude pregnant women from study participation. A careful metal screening history will be taken from each participant to assess the possibility of metal devices/implants and will be reviewed by the PI, MRI technician and/or clinical staff who have had extensive training and experience with MRI safety. If the screening yields information that raises a question of safety, the participant will be asked to provide the appropriate documentation (i.e., film) before they are allowed to participate. In addition, participants will be asked to empty their pockets and will be screened with a hand-held ferromagnetic-detector wand. Participants will wear earplugs and/or sound-dampening headphones to decrease the intensity of the scanner noise. Prior exposure to pictures of the scanner, getting into the mock scanner, and seeing others in the scanner, often reduces psychological discomfort or identifies people for whom scanning is not appropriate.

Subjects will have weekly contact with study staff while receiving doxazosin, which will allow for frequent monitoring of side effects. Standing and sitting/supine blood pressure may be recorded at weekly visits. Subjects will be taught about potential side effects of doxazosin and will be closely followed by psychiatrists (Drs. [name] and [name]), a physician assistant, and other members of the research team. The instrumentation used for physiological recordings meets all safety standards for non-invasive recordings, and participants are located out of reach of any AC-powered devices in the laboratory. Our research group has extensive experience administering medications to and monitoring clinical populations including Veterans with comorbid PTSD and substance use disorders (i.e., alcohol, cocaine, marijuana and opioid use disorders).

Research Monitor. The Research Monitor, [name], will oversee the safety of the research and report observations/findings to the IRB or a designated institutional official. The Research Monitor will review all unanticipated problems involving risks to subjects or others associated with the protocol and provide an independent report of the event to the IRB. The Research Monitor may discuss the research protocol with the investigators; shall have authority to stop a research protocol in progress, remove individual human subjects from a research protocol, and take whatever steps are necessary to protect the safety and well-being of human subjects until the IRB can assess the monitor's report; and shall have the responsibility to promptly report their observations and findings to the IRB or other designated official and the HRPO.

